6.3 Subject Population(s) for Analysis

The primary analysis will be intention to treat (ITT). A secondary analysis will be considered using a per protocol (PP) analysis.

7 Safety and Adverse Events

7.1 Definitions

Unanticipated Problems Involving Risk to Subjects or Others (UPIRTSO)

Any unanticipated problem or adverse event that meets the following three criteria:

- Serious: Serious problems or events that results in significant harm, (which may be physical, psychological, financial, social, economic, or legal) or increased risk for the subject or others (including individuals who are not research subjects). These include: (1) death; (2) life threatening adverse experience; (3) hospitalization - inpatient, new, or prolonged; (4) disability/incapacity - persistent or significant; (5) birth defect/anomaly; (6) breach of confidentiality and (7) other problems, events, or new information (i.e. publications, DSMB reports, interim findings, product labeling change) that in the opinion of the local investigator may adversely affect the rights, safety, or welfare of the subjects or others, or substantially compromise the research data, AND
- Unanticipated: (i.e. unexpected) problems or events are those that are not already described as potential risks in the protocol, consent document, not listed in the Investigator's Brochure, or not part of an underlying disease. A problem or event is "unanticipated" when it was unforeseeable at the time of its occurrence. A problem or event is "unanticipated" when it occurs at an increased frequency or at an increased severity than expected, AND
- Related: A problem or event is "related" if it is possibly related to the research procedures.

Adverse Event

An untoward or undesirable experience associated with the use of a medical product (i.e. drug, device, biologic) in a patient or research subject.

Serious Adverse Event

Adverse events are classified as serious or non-serious. Serious problems/events can be well defined and include;

- death
- life threatening adverse experience
- hospitalization
- inpatient, new, or prolonged; disability/incapacity
- persistent or significant disability or incapacity
- birth defect/anomaly

and/or per protocol may be problems/events that in the opinion of the sponsorinvestigator may have adversely affected the rights, safety, or welfare of the subjects or others, or substantially compromised the research data.

All adverse events that do not meet any of the criteria for serious, should be regarded as **non-serious adverse events**.

Adverse Event Reporting Period

For this study, the study treatment follow-up period is defined as the time of consent until 30 days following hospital discharge or until the removal of the chest tube if after 30 days.

Preexisting Condition

A preexisting condition is one that is present at the start of the study. A preexisting condition should be recorded as an adverse event if the frequency, intensity, or the character of the condition worsens during the study period.

General Physical Examination Findings

At screening, any clinically significant abnormality should be recorded as a preexisting condition. At the end of the study, any new clinically significant findings/abnormalities that meet the definition of an adverse event must also be recorded and documented as an adverse event.

Post-study Adverse Event

All unresolved adverse events should be followed by the sponsor-investigator until the events are resolved, the subject is lost to follow-up, or the adverse event is otherwise explained. At the last scheduled visit, the sponsor-investigator should instruct each subject to report, to the sponsor-investigator, any subsequent event(s) that the subject, or the subject's personal physician, believes might reasonably be related to participation in this study.

Abnormal Laboratory Values

A clinical laboratory abnormality should be documented as an adverse event if it requires active management or treatment.

Hospitalization, Prolonged Hospitalization or Surgery

Any adverse event that results in hospitalization or prolonged hospitalization should be documented and reported as a serious adverse event unless specifically instructed otherwise in this protocol. Any condition responsible for surgery should be documented as an adverse event if the condition meets the criteria for an adverse event.

Neither the condition, hospitalization, prolonged hospitalization, nor surgery are reported as an adverse event in the following circumstances:

 Hospitalization or prolonged hospitalization for diagnostic or elective surgical procedures for a preexisting condition. Surgery should **not** be reported as an outcome of an adverse event if the purpose of the surgery was elective or diagnostic and the outcome was uneventful.

7.2 Recording of Adverse Events

At each contact with the subject, the study team must seek information on adverse events by specific questioning and, as appropriate, by examination. Information on all adverse events should be recorded immediately in the source document, and also in the appropriate adverse event section of the case report form (CRF). All clearly related signs, symptoms, and abnormal diagnostic, laboratory or procedure results should recorded in the source document.

Adverse event data related to the indwelling chest tube, valve, ongoing air leak, or antibiotic use (group one) occurring during the study period must be recorded. The clinical course of each event should be followed until resolution, stabilization, or until it has been ultimately determined that the study treatment or participation is not the probable cause. Serious adverse events that are still ongoing at the end of the study period must be followed up, to determine the final outcome. Any serious adverse event that occurs during the Adverse Event Reporting Period and is considered to be at least possibly related to the study treatment or study participation should be recorded and reported immediately.

CTCAE Version 5.0 (v5.0: November 27, 2017) will be used to standardize classification and grading of Adverse Events.

7.3 Reporting of Serious Adverse Events and Unanticipated Problems

When an adverse event has been identified, the study team will take appropriated action necessary to protect the study participant and then complete the Study Adverse Event Worksheet and log and notify the coordinating site. The sponsor-investigator will evaluate the event and determine the necessary follow-up and reporting required.

7.3.1 Sponsor-Investigator reporting: notifying the Mayo IRB

The sponsor-investigator will report to the Mayo IRB any UPIRTSOs and Non-UPIRTSOs according to the Mayo IRB Policy and Procedures.

According to Mayo IRB Policy any serious adverse event (SAE) which the Principal Investigator has determined to be a UPIRTSO must be reported to the Mayo IRB as soon as possible but no later than 5 working days after the investigator first learns of the problem/event.

Information collected on the adverse event worksheet (and entered in the research database) will include:

- Subject's number
- The date the adverse event occurred:
- Description of the adverse event:
- Relationship of the adverse event to the research:
- If the adverse event was expected:
- The severity of the adverse event:
- If any intervention was necessary:
- Resolution: (was the incident resolved spontaneously, or after discontinuing treatment)
- Date of Resolution:

The sponsor-investigator will review all adverse event reports to determine if specific reports need to be made to the IRB and FDA. The sponsor-investigator will sign and date the adverse event report when it is reviewed. For this protocol, only directly related SAEs/UPIRTSOs will be reported to the IRB.

Relationship Index Example

The relationship of an AE to the study procedures is a clinical decision by the sponsorinvestigator (PI) based on all available information at the time of the completion of the CRF and is graded as follows:

1. Not related: a reaction for which sufficient information exists to indicate that the etiology is unrelated to the study procedures; the event is clearly related to other factors such as the subject's clinical state, therapeutic intervention or concomitant therapy.

2. Unlikely: a clinical event, including laboratory test abnormality, with a temporal relationship to the study procedures which makes a causal relationship improbable and in which other drugs, chemicals, or underlying disease provide plausible explanations.

3. Possible: a clinical event, including laboratory test abnormality, with a reasonable time sequence to administration of the study procedures but which could also be explained by concurrent disease or other drugs or chemicals; information on drug withdrawals may be lacking are unclear.

4. Probable: a clinical event including laboratory test abnormality, with a reasonable time sequence to the study procedures, unlikely to be attributed to concurrent disease or other drugs or chemicals.

5. Definite: a reaction that follows a reasonable temporal sequence from administration of the study procedures.

Severity Index

The maximum intensity of an AE should be graded according to the definitions below and recorded in details as indicated on the CRF. If the intensity of an AE changes over a number of days, then separate entries should be made having distinct onset dates.

1. Mild: AEs are usually transient, requiring no special treatment, and do not interfere with patient's daily activities.

2. Moderate: AEs typically introduce a low level of inconvenience or concern to the patient and may interfere with daily activities, but are usually ameliorated by simple therapeutic measures.

3. Severe: AEs interrupt a patient's usual daily activity and traditionally require systemic drug therapy or other treatment.

7.4 Medical Monitoring

It is the responsibility of the Principal Investigator to oversee the safety of the study at his/her site. This safety monitoring will include careful assessment and appropriate reporting of adverse events as noted above, as well as the construction and implementation of a site data and safety-monitoring plan (see section 10 "Study Monitoring, Auditing, and Inspecting"). Medical monitoring will include a regular assessment of the number and type of serious adverse events.

7.4.1 Data and Safety Monitoring Board

The Mayo Clinic Department of Surgery Data Safety and Monitoring Board (DSMB) will evaluate and adjudicate Serious Adverse Events and Specified Adverse Events as reported by the Investigators for relatedness to device and procedure. The DSMB will also be given the listings of all other adverse events (not Serious and not Specified) for review and to determine if additional adjudication is required. The DSMB will be given any information requested to adjudicate adverse events. The DSMB will meet twice yearly, or more or less often as needed.

7.4.2 Early Stopping Rules

The study will be paused temporarily until the DSMB can review if any patient is permanently disabled, has life threatening consequences (defined as Grade 4 adverse event by CTCAE Version 5.0), or dies in a manner that could be consistent with the antibiotic usage. The study will be continued if the event is demonstrably unrelated to subject's usage of antibiotics (for example, caused by indwelling chest tube or a surgical complication).

8 Data Handling and Record Keeping

8.1 Confidentiality

Information about study subjects will be kept confidential and managed according to the requirements of the Health Insurance Portability and Accountability Act of 1996 (HIPAA). Those regulations require a signed subject authorization informing the subject of the following:

- What protected health information (PHI) will be collected from subjects in this study
- · Who will have access to that information and why
- Who will use or disclose that information
- The rights of a research subject to revoke their authorization for use of their PHI.

In the event that a subject revokes authorization to collect or use PHI, the investigator, by regulation, retains the ability to use all information collected prior to the revocation of subject authorization. For subjects that have revoked authorization to collect or use PHI, attempts should be made to obtain permission to collect at least vital status (long term survival status that the subject is alive) at the end of their scheduled study period.

8.2 Source Documents

Source data is all information, original records of clinical findings, observations, or other activities in a clinical trial necessary for the reconstruction and evaluation of the trial. Source data are contained in source documents. Examples of these original documents, and data records include: hospital records, clinical and office charts, laboratory notes, memoranda, subjects' diaries or evaluation checklists, pharmacy dispensing records, recorded data from automated instruments, copies or transcriptions certified after verification as being accurate and complete, microfiches, photographic negatives, microfilm or magnetic media, x-rays, subject files, and records kept at the pharmacy, at the laboratories, and at medico-technical departments involved in the clinical trial.

8.3 Case Report Forms

The study case report form (CRF) is the primary data collection instrument for the study. All data requested on the CRF must be recorded. All missing data must be explained. If a space on the CRF is left blank because the procedure was not done or the question was not asked, write "N/D". If the item is not applicable to the individual case, write "N/A". All entries should be printed legibly in black ink. If any entry error has been made, to correct such an error, draw a single straight line through the incorrect entry and enter the correct data above it. All such changes must be initialed and dated. Do not erase or use "white-out" for errors. For clarification of illegible or uncertain entries, print the clarification above the item, then initial and date it. If the reason for the correction is not clear or needs additional explanation, neatly include the details to justify the correction.

Data Management

Data will be entered into a Medidata RAVE database. Medidata RAVE is a secure, customizable Web application designed for collecting study data. Once collected, data can be automatically exported to Microsoft Excel or several common statistical software packages (SPSS, SAS, R and Stata) for analysis. Randomization will take place in the Balance module of Medidata RAVE and will be stratified by enrollment site.

Data Processing

Data will be entered by each research site. Data will be analyzed at the Mayo Clinic Rochester.

Data Security and Confidentiality

Medidata RAVE is a secure database which requires individual log on. Data from each site is only accessible by the site and the data managing site, Mayo Clinic Rochester.

Data Quality Assurance

Medidata RAVE has built in data checks. Source documents may be requested by the data management site, Mayo Clinic Rochester, in order to verify data if needed.

8.4 Records Retention

The sponsor-investigator will maintain records and essential documents related to the conduct of the study. These will include subject case histories and regulatory documents.

Subject names or other directly identifiable information will not appear on any reports, publications, or other disclosures of clinical study outcomes.

The sponsor-investigator will retain the specified records and reports for;

- 1. Up to 2 years after the marketing application is approved for the drug; or, if a marketing application is not submitted or approved for the drug, until 2 years after shipment and delivery of the drug for investigational use is discontinued and the FDA has been so notified. OR
- As outlined in the Mayo Clinic Research Policy Manual "Retention of and Access to Research Data Policy" http://mayocontent.mayo.edu/research-policy/MSS_669717 whichever is longer.

9 Study Monitoring, Auditing, and Inspecting

9.1 Study Monitoring Plan

The investigator will allocate adequate time for such monitoring activities. The investigator will also ensure that the monitor or other compliance or quality assurance reviewer is given access to all the study-related documents and study related facilities (e.g. pharmacy, diagnostic laboratory, etc.), and has adequate space to conduct the monitoring visit.

9.2 Auditing and Inspecting

The investigator will permit study-related monitoring, audits, and inspections by the IRB, the sponsor, and government regulatory agencies, of all study related documents (e.g. source documents, regulatory documents, data collection instruments, study data etc.). The investigator will ensure the capability for inspections of applicable study-related facilities (e.g. pharmacy, diagnostic laboratory, etc.).

Participation as an investigator in this study implies acceptance of potential inspection by government regulatory authorities and applicable compliance offices.

10 Ethical Considerations

This study is to be conducted according to United States government regulations and Institutional research policies and procedures.

This protocol and any amendments will be submitted to a properly constituted local Institutional Review Board (IRB), in agreement with local legal prescriptions, for formal approval of the study. The decision of the IRB concerning the conduct of the study will be made in writing to the sponsor-investigator before commencement of this study.

All subjects for this study will be provided a consent form describing this study and providing sufficient information for subjects to make an informed decision about their participation in this study. This consent form will be submitted with the protocol for review and approval by the IRB for the study. The formal consent of a subject, using the Approved IRB consent form, must be obtained before that subject undergoes any study procedure. The consent form must be signed by the subject and the individual obtaining the informed consent.

11 Study Finances

14.1 Patient Chest Tube Diary

Month:							
Sunday	Monday	Tuesday	Wednesday	Thursday	Friday	Saturday	
Did you take your antibiotic today? Yes No Does your chest tube have an air leak? Yes, looks differently than before Yes, looks the same as before No	Did you take your antibiotic today? Yes No Does your chest tube have an air leak? Yes, looks differently than before Yes, looks the same as before No	Did you take your antibiotic today? Yes No Does your chest tube have an air leak? Yes, looks differently than before Yes, looks the same as before No	Did you take your antibiotic today? Yes No Does your chest tube have an air leak? Yes, looks differently than before Yes, looks the same as before No	Did you take your antibiotic today? Yes No Does your chest tube have an air leak? Yes, looks differently than before Yes, looks the same as before No	Did you take your antibiotic today? Yes No Does your chest tube have an air leak? Yes, looks differently than before Yes, looks the same as before No	Did you take you antibiotic today?	
Comments:	Comments:	Comments:	Comments:	Comments:	Comments:	Comments:	

Group 2: Patient Chest Tube Diary

Protocol #: _____ Participant ID: _____

Physician: _____

Instructions for you: This is a calendar for you to record information about your chest tube everyday.

If you have any questions, please contact: ______

Month:

Sunday Monday		Tuesday	Wednesday	Thursday	Friday	Saturday
Does your chest tube have an air leak? Yes, looks differently than before Yes, looks the same as before No Comments:	Does your chest tube have an air leak? I Yes, looks differently than before Yes, looks the same as before No Comments:	Does your chest tube have an air leak? Yes, looks differently than before Yes, looks the same as before No Comments:	Does your chest tube have an air leak? Yes, looks differently than before Yes, looks the same as before No Comments:	Does your chest tube have an air leak? I Yes, looks differently than before Yes, looks the same as before No Comments:	Does your chest tube have an air leak? I Yes, looks differently than before Yes, looks the same as before No Comments:	Does your chest tube have an air leak? I Yes, looks differently than before Yes, looks the same as before No Comments:
Patient Signature		Date				

Date

Study Coordinator Signature

Date the chest tube was removed:

14.2 Twice Weekly Telephone Script

Twice Weekly Telephone Script

Protocol Title: A Randomized Study Evaluating Patients Discharged with Indwelling Chest Tube and Valve IRB #: 17-007774

Principal Investigator: [name]

Introduction:

Hello, this is _____ calling from the Mayo Clinic in Rochester, Minnesota (if out of state). May I please speak to _____?

***If the participant is there continue with the script.

***If the participant is not there, ask when it would be a good time to speak with ?

Describe the Reason for the Call:

We are calling to check in on the progress of your air leak and indwelling chest tube and valve. If you may recall you agreed to participate in A Randomized Study Evaluating Patients Discharged with Indwelling Chest Tube and Valve and you were randomized to the group which receives twice weekly telephone calls to follow up on your indwelling chest tube.

Does your indwelling chest tube with valve have an air leak?

- 🗆 No
- Yes

If yes, has the air leak changed?

🗆 No

Yes

If yes, please explain:

Is there anything else we need to know about your indwelling chest tube and valve?

Closing

Thank you for participating in our research study. Please understand that your answers will remain confidential. Give them some follow-up contact information (name and telephone number) in case they think of any more questions afterwards.

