1.3 Risks and Benefits

All study interventions could be considered standard of care.

Cerfolio and colleagues cite the use of oral antibiotics while the chest drain is in place but they do not address any risks or benefits but state it is merely their preference (3). In the study conducted by Reinersman and colleagues, the 27 patients discharging with indwelling chest tubes in place that received prophylactic antibiotics at discharge were found to have no complications from the antibiotics (15). Cerfolio, Reinersman and colleagues have reported that an air leak lasting longer than 7 days leads to an increased risk of empyema (14, 15).

The Surgical Care Improvement Project (SCIP) Performance Measures endorse pprophylactic antibiotics discontinued within 24 hours after surgery end-time. There is no significant evidence showing a benefit to continuing antibiotic usage beyond 24 hours. Prolonged administration of antibiotic usage may increase the risk of drug resistance and secondary infections, such as *Clostridium difficile* (16).

2 Study Objectives

Primary Objective

To assess the efficacy of antibiotics and closer monitoring on decreasing empyema in patients discharging with a chest tube and valve in place as measured by documented empyema following discharge.

Secondary Objective

To assess the efficacy of antibiotics and closer monitoring on decreasing hospital readmissions while the chest tube and valve are in place as measured by readmission to the hospital following hospital discharge after the initial surgical intervention.

3 Study Design

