5.5 Off Study

Subjects will be followed for 30 days following discharge from the hospital or until the chest tube has been removed if it remains in place for more than 30 days post hospital discharge. The patient will be instructed to return their Patient Chest Tube Diary at their next visit or via mail if they did not use the electronic app. A telephone call may be made in order to remind the participants to return their daily diary. Attachment 14.3.

Schedule of Events						
Study Activity	Visit 1	Visit 2	Daily Diary	Twice Weekly Calls ^a	Off Study	
Informed Consent	х					
Air Leak Status	Х					
Surgical History	Х					
Patient Education		х				
Patient Chest Tube Diary			x			
Telephone Assessment				Х		
Adverse Event Evaluation			Х	Х	х	
a: Group 1 only. b: Includes microbiology assessment of infection if done as part of clinical care and data is available.						

6 Statistical Plan

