14.3 Diary Return Telephone Script

Diary Return Telephone Script

Protocol Title: A Randomized Study Evaluating Patients Discharged with Indwelling Chest Tube and Valve IRB #: 17-007774

Principal Investigator: [name]

Introduction:

Hello, this is _____ calling from the Mayo Clinic in Rochester, Minnesota (if out of state). May I please speak to _____?

***1f the participant is there continue with the script.

***If the participant is not there, ask when it would be a good time to speak with ?

Describe the Reason for the Call:

As you may recall you agreed to participate in A Randomized Study Evaluating Patients Discharged with Indwelling Chest Tube and Valve and you were asked to complete a daily diary about your indwelling chest tube. We are calling to confirm that if your chest tube has been removed that you have returned your Patient Chest Tube Diary.

Has your chest tube been removed?

🗆 No

If no, as a reminder when it has been removed please note that on your diary and send it back in the provided envelope. If you do not have your envelope we would be happy to send one out to you.

Yes

If yes, have you returned your diary?

🗆 No

If no, as a reminder please send it back in the provided envelope. If you do not have your envelope we would be happy to send one out to you.

□ Yes

If yes, thank you so much for returning the diary.

Closing

Thank you for participating in our research study. Please understand that your answers will remain confidential. Give them some follow-up contact information (name and telephone number) in case they think of any more questions afterwards.

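### Section 7.2 and the Schedule of Events require adverse-event evaluation at contacts whose scripts and visible diary items contain no adverse-event question, so non-serious antibiotic harms rest on volunteering or on unequal off-script asking

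*Protocol*

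**What the plan says.** Protocol section 7.2 (Recording of Adverse Events) sets the duty: "At each contact with the subject, the study team must seek information on adverse events by specific questioning and, as appropriate, by examination". It also fixes the scope of mandatory recording, in a sentence that begins: "Adverse event data related to the indwelling chest tube, valve, ongoing air leak, or antibiotic use (group one) occurring during the study period must be". Antibiotic events in Group 1 are therefore expressly included.

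The Schedule of Events under section 5.5 has a row "Adverse Event Evaluation" with three marks. By column order these fall at the daily diary, the twice-weekly calls and off study. Only the calls column is restricted to Group 1.

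The instruments are in section 14:

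- **14.2, twice-weekly calls (Group 1).** The stated purpose is "We are calling to check in on the progress of your air leak and indwelling chest tube and valve". The caller asks whether there is a leak, whether it has changed, and "Is there anything else we need to know about your indwelling chest tube and valve".
- **14.3, diary return.** The stated purpose is "We are calling to confirm that if your chest tube has been removed that you have returned your Patient Chest Tube Diary". Section 5.5 makes this reminder call optional.
- **14.1, diaries.** Group 1 records antibiotic intake and leak status each day; Group 2 records leak status. Both have a free comments space.

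**The concern.** The body of the protocol and its attachments disagree about what happens at a study contact. A coordinator who reads out 14.2 word for word never mentions the antibiotic or any symptom, and even the open question is confined to the device.

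This matters because an oral antibiotic is half of the tested intervention. Section 1.3 names its possible harms: "Prolonged administration of antibiotic usage may increase the risk of drug resistance and secondary infections", with *C. difficile* as the example. It also says there is no significant evidence of benefit beyond 24 hours after surgery, and the discharge-antibiotic safety experience it cites for these patients comes from 27 people. Section 7.4.1 promises the DSMB listings of non-serious events, and those listings can be no more complete than the questions behind them.

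The second issue is comparability. Calls go to Group 1 only (section 5.4), so questioning that staff improvise on those calls has no counterpart in Group 2.

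**Working it through.** The check is a comparison of texts: what is required at each contact against what the instrument asks.

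| Contact | Arm | Adverse-event evaluation in the Schedule | What the instrument asks | Adverse-event questions seen |
|---|---|---|---|---|
| Daily diary (14.1, Group 1) | 1 | Yes | Antibiotic taken, leak, comments | 0 |
| Daily diary (14.1, Group 2) | 2 | Yes | Leak, comments | 0 |
| Twice-weekly call (14.2) | 1 | Yes | Leak present, leak changed, anything else about tube and valve | 0 |
| Off study (14.3 is the only script supplied) | Both | Yes | Tube removed, diary returned | 0 |

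The source of the requirement differs by row. Section 7.2 is addressed to the study team, so it governs the calls and any off-study contact. The diary is completed by the patient, so there the requirement comes from the Schedule mark alone. In the copy available, the heading of the Group 1 diary and part of its Saturday cell are missing; its six complete daily cells contain no adverse-event item.

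Two consequences follow.

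1. *Scripts followed as written.* A non-serious antibiotic event that brings no recorded medical care is known only if the patient volunteers it.
2. *Staff ask off-script to satisfy 7.2.* The question is then put at each Group 1 call, while Group 2 has no calls.

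An illustration shows how this could affect counts. The rates are assumptions; the protocol gives none. Take 560 / 2 = 280 patients per arm (equal arms, as section 6.1 implies), a true event proportion r and a probability v that an event becomes known. The expected known count is 280 × r × v.

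| r (assumed) | v = 1 | v = 0.5 | v = 0.2 |
|---|---|---|---|
| 0.01 | 2.8 | 1.4 | 0.56 |
| 0.02 | 5.6 | 2.8 | 1.12 |
| 0.05 | 14 | 7 | 2.8 |

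Read along a row, the table shows the loss when events must be volunteered. It also shows the distortion if one arm is questioned and the other is not. With the same true 5% in both arms, v = 1 in one and v = 0.5 in the other would give 14 against 7 known events with no real difference. How far v falls below 1, or differs by arm, cannot be found from the protocol.

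**The case against.** The strongest reply is that a script does not cancel a duty. Section 7.2 binds staff whatever 14.2 says, and nothing forbids them to ask more than the script. There are other routes too: an adverse-event section in the CRF (7.2), an adverse-event worksheet and log (7.3), comments spaces in both diaries, and laboratory results and hospital admissions from source documents and the medical record (3.6). This stands. A reader might infer that antibiotic harm would be found only by accident; the documents do not support that. What is exposed is mainly the non-serious event that reaches no record.

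A reader might also infer that Group 2 is never asked about events. The Schedule marks off-study evaluation without restricting it to Group 1, section 5.5 provides for diary return at a next visit, and section 7.1 refers to a last scheduled visit. Group 2 does have an adverse-event contact; what is missing is a question written for it. Likewise 14.3 is an optional reminder and is not named as the instrument for off-study evaluation, so its silence does not prove that the evaluation is absent.

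A third tempting step is to say that the pause rule in 7.4.2 would fail. Its triggers are death, permanent disability and Grade 4 events, which would mostly surface through care whatever the script says.

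Finally, multiplying calls per patient by patients would give only a ceiling. The protocol does not say when calls stop, and section 3.1 follows subjects until tube removal.

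None of these points supplies the specific questioning that 7.2 requires. An open prompt limited to the device, or a blank comments space, is not that.

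**Conclusion.** The point holds as an inconsistency between section 7.2 and the Schedule on one side and Attachments 14.1 to 14.3 on the other. Three contact types are marked for adverse-event evaluation, and none of the four instruments shows an adverse-event question. The effect is confined to non-serious antibiotic events that lead to no recorded care, and to the fairness of any comparison of harms between arms. The analyses of empyema and readmission do not depend on it.

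The conclusion rests on two assumptions: that the missing part of the Group 1 diary contains no adverse-event item, and that no other contact form exists outside the attachments listed in section 14. If the Group 1 diary heading does ask about side effects, the point still holds for 14.2, for the off-study contact and for the inequality between arms. It should be corrected, but it does not threaten the trial's main result.

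**What to change.** Reconcile section 7.2, the Schedule of Events and Attachments 14.1 to 14.3:

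- Add to 14.2 a specific adverse-event question that expressly includes antibiotic-related events.
- Put one identical adverse-event question to both arms at the off-study contact already marked in the Schedule. It can be asked at the diary-return visit, or in 14.3 if that call is made for everyone not seen in person.
- State that any between-arm comparison of harms rests on this common off-study item. Events found through Group 1 calls can be listed for that arm but should not be set against Group 2.
- For 14.1, say whether the comments space is the intended diary evaluation, or amend the Schedule mark.

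A daily symptom checklist in the Group 2 diary is not recommended here. Section 3.1 defines control as waiting for the patient to make contact, and daily prompting could weaken the monitoring contrast under test.

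The cost is script wording, one CRF field, and a short call that becomes routine instead of optional for those not seen in person. No new visit is needed. What staff do after a positive answer is for the sponsor to state.
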